8.3 WITHDRAWAL CRITERIA

Once SAR421869 has been administered it cannot be removed, therefore patients are unable to withdraw from the study treatment. However, an individual may withdraw consent from any study related procedures at any time throughout the study and this will not affect the standard of care they receive.

Individual patients may also be withdrawn under the following circumstances:

- The patient experiences a serious or severe adverse event that prevents him/her from continuing.
- The patient incurs a significant protocol violation. Withdrawal will be judged by the Investigator and the Medical Monitor on a case by case basis.
- The patient requests early discontinuation.
- Request of the Sponsor.
- Investigator's request (eg, if the Investigator considers that the patient's health is compromised by remaining in the study or the patient is not sufficiently co-operative).
- The patient is lost to follow-up. (All attempts will be made to locate patients lost to follow-up).

Any patient that is withdrawn early from the study will be encouraged to consent to an open-label, long-term follow-up study. If the patient withdraws or is withdrawn from the study, the Week 48 procedures should be completed if possible.

The long-term safety follow-up will be described in a separate protocol which will be submitted to regulatory agencies and Institutional Review Boards/Independent Ethics Committees for approval.

The open-label, follow-up study has been designed to capture the essential safety data pertinent to gene therapy follow-up, as well as key efficacy assessments, whilst providing the patient with a degree of flexibility for minimizing inconvenience. The long-term follow-up protocol will also permit patients to receive alternative treatment during their participation while allowing for safety follow-up.

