8.4 STUDY STOPPING CRITERIA

The following are considered stopping criteria:

- Prolonged anterior chamber inflammation and/or prolonged posterior chamber inflammation continuing without signs of resolution 28 days after SAR421869 administration.

Criteria for suspending enrolment or further study conduct are defined in the DSMB charter and all events will be reviewed by the DSMB.

In the event of early study termination all patients who have been dosed with SAR421869 will continue to be followed up as per protocol.

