11.8 WITHDRAWALS DUE TO ADVERSE EVENTS

Once SAR421869 has been administered it cannot be removed from the eye. A patient may withdraw consent from follow-up monitoring only. If an AE occurs the patient will be followed up until the AE is resolved or has stabilized. As the primary endpoint of this study is safety and tolerability the patient will continue to be monitored.

Withdrawal from the study and reason for withdrawal must be documented in the CRF.

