6.2 Primary Data Set

The primary data set to be used to prepare the final analysis and DSMB reports will include data from all eligible patients, regardless of adherence to the protocol. However, since patients receive only a single treatment, adherence to the protocol will only be affected if patients drop out of the study, are lost to follow-up or if patients are seen outside of the visit windows as defined in the study protocol. If a patient withdraws from the study, the Week 48 procedures will be completed where possible.

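### Protocol 8.3 lets a dosed patient be withdrawn after an adverse event, which conflicts with 11.8 and weakens the 12-month safety follow-up

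*Protocol*

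**What the plan says.** Protocol 8.3 opens by noting that the product cannot be taken out once given, so nobody can withdraw from treatment. It then lists circumstances in which an individual may be withdrawn, without saying whether they apply before or after dosing:

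- "The patient experiences a serious or severe adverse event that prevents him/her from continuing"
- "The patient incurs a significant protocol violation", judged case by case by the investigator and the medical monitor
- "Request of the Sponsor", with no condition attached
- investigator request, for example "if the Investigator considers that the patient's health is compromised by remaining in the study or the patient is not sufficiently co-operative"
- the patient's own request, and loss to follow-up

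For anyone withdrawn, 8.3 asks for the Week 48 procedures where possible and encourages consent to the separate long-term study.

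Protocol 11.8, on withdrawals due to adverse events, says: "A patient may withdraw consent from follow-up monitoring only". It requires an adverse event to be followed until it resolves or stabilizes, and adds: "As the primary endpoint of this study is safety and tolerability the patient will continue to be monitored". It also asks for any study withdrawal and its reason to be recorded.

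Two other places show the general intent. Under Protocol 8.4, if the study is terminated early, "all patients who have been dosed with SAR421869 will continue to be followed up as per protocol". Under SAP 6.2 the primary data set "will include data from all eligible patients, regardless of adherence to the protocol". SAP 6.3 keeps all collected data and imputes nothing.

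**The concern.** After a single dose that cannot be reversed, withdrawal can only mean that study observation ends. A site that follows 8.3 may end the visits of a dosed patient because of an adverse event. A site that follows 11.8 may not.

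The primary endpoint is adverse-event incidence over 12 months, together with clinically important changes in safety assessments that SAP 7.3 analyses at Week 48. Withdrawal because of a serious or severe event is related to outcome, so any later data that go missing come from a patient already doing badly, and the dose can look safer than it is. Protocol section 7 also allows up to three replacements for patients who do not complete the first six months, whatever the reason. A patient lost in this way could therefore be succeeded by one with a cleaner record.

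**Working it through.** **Step 1. Each ground in 8.3 against 11.8**

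| Ground in 8.3 | What 11.8 says | Result |
|---|---|---|
| Serious or severe event that prevents continuing | Event followed to resolution or stabilization; patient continues to be monitored | Conflict |
| Protocol violation | Not addressed | No direct conflict |
| Sponsor request | Not addressed | No direct conflict |
| Poor co-operation | Not addressed | No direct conflict |

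**Step 2. What is kept and what can be lost**

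- Kept: the triggering event is already in the incidence count, and 11.6 and 11.8 require it to be followed. SAP 6.3 keeps the data collected so far.
- Lost, adverse events: under 11.6, events are recorded up to that patient's end of study. After that, 11.6.1 asks only for serious events considered caused by the product. New non-serious events, and serious events not judged related, can go unrecorded.
- Lost, visits: after Week 4 the schedule for Cohorts 1-3a has four visits (Weeks 12, 24, 36, 48), and the schedule for Cohorts 3b-5 has three (Weeks 12, 24, 48).
- Lost, endpoint: the schedule notes let the Week 48 procedures serve as the early-termination visit. A value labelled Week 48 may have been taken much earlier, or not at all. The output list in the memorandum attached to the SAP tabulates BCVA change and elevated IOP specifically at Week 48.

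**Step 3. The plan's own counts**

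- Part A by cohort (Protocol Table 3): 3 + 3 + 1 + 2 + 3 + 3 = 15, the stated minimum.
- Completers (Protocol section 8): 3 + 3 + 9 + 6 + 6 = 27 and 24 + 6 + 6 = 36, as stated.

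**Step 4. Share of a dose level carried by one patient**

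Planned Part A patients by measured dose (TU/eye, Table 3):

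- 2.1×10^4: 3 patients, 1/3 = 33%
- 1.1×10^5: 3 patients, 1/3 = 33%
- 0.33×10^6: 1 (Cohort 3a) + 3 (Cohort 3b) = 4 patients, 1/4 = 25%
- 1.4×10^6: 3 patients, 1/3 = 33%
- 2.4×10^6: 2 patients, 1/2 = 50%

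**Step 5. Illustration for a cohort of 3**

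The documents give no event risk or withdrawal rate, so the risks of 10% to 30% are assumptions. They concern events that start after the withdrawal.

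- Chance of seeing at least one such event, 1 − (1 − p)^n, as n falls from 3 to 2: 27.1% to 19.0% at p = 10%; 48.8% to 36.0% at 20%; 65.7% to 51.0% at 30%.
- One-sided 95% upper limit with no events, 1 − 0.05^(1/n): 63.2% for 0/3, 77.6% for 0/2.
- If the withdrawn patient is the one who would have had the later event, 1/3 becomes 0/2, or 0/3 if that patient stays in the denominator.
- Observation time, (2 × 48 + w)/(3 × 48), for withdrawal at week w: 69% at Week 4, 75% at Week 12, 83% at Week 24, 92% at Week 36.

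**The case against.** The strongest reply is that the protocol already protects the data that matter. The adverse-event ground applies only when the event prevents the patient from continuing. The event is counted and followed under 11.6 and 11.8, and 11.6.1 takes later serious events judged related. An early-termination visit exists and the long-term study is offered. Even severe intraocular inflammation, the obvious example, is an event of special interest under 11.5 once it passes the stated step threshold, so it would be followed. All of this stands, and it is why a reader who infers that 8.3 removes primary-endpoint follow-up goes too far.

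A reader might also infer that 11.8 makes the patient's own decision the only way to leave. Its sentence on consent can equally be read as limiting what can be withdrawn from (monitoring, not treatment), and 11.8 itself provides for recording a withdrawal. Its title confines it to adverse events, so it does not contradict the other grounds. Nor are 8.4 and SAP 6.2 contradictions: one covers early termination of the whole study, the other defines a data set and in the same paragraph provides for patients who withdraw. They show intent and no more.

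What survives is the conflict on the adverse-event ground and the loss in step 2. The safeguards do not close that gap. The Week 48 procedures are conditional, and the long-term study needs separate consent and need only see patients every six months. Whether that study could stand in for the missed visits depends on a protocol that is not part of these documents.

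**Conclusion.** The point holds as a conflict to be reconciled and a weakness in follow-up, and should be corrected. For adverse events, 8.3 and 11.8 give sites different instructions about a dosed patient. For violation, sponsor request and poor co-operation the objection is one of design: none of these justifies ending observation after an irreversible dose.

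One withdrawal costs 25% to 50% of a Part A dose level's Week 48 data. This assumes that the Week 48 visit is not done and that Cohorts 3b and 3c are dosed as planned. A reader might put the upper end at 100%, because one Cohort 3a patient received 0.33×10^6 TU. The plan does not support that, since Cohort 3b adds three patients at the same measured dose. The adverse-event shell in the memorandum attached to the SAP groups by cohort with N=3, where one patient is 33%.

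The argument that the loss falls on the patients who did worst applies to the adverse-event ground and need not apply to the others. The documents do not say how often withdrawal is expected, so step 5 shows sensitivity only and does not predict a bias.

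**What to change.** Split 8.3 into before dosing and after dosing, and reconcile the second part with 11.8. After dosing, state that an adverse event, a protocol violation, a sponsor request or incomplete co-operation does not by itself end follow-up. The patient stays on the visit schedule to Week 48 for adverse-event recording and whatever examinations he or she can do. Follow-up ends early only if the patient withdraws consent, dies or is lost to follow-up.

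Keep the investigator's discretion to omit procedures or visits that would compromise the patient's health, with adverse-event follow-up continuing. Simply deleting the investigator ground would take away a patient protection.

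The cost is one protocol paragraph and, for a few patients, visits that are already in the schedule. The patient's right to withdraw consent does not change.

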8.4 STUDY STOPPING CRITERIA

The following are considered stopping criteria:

- Prolonged anterior chamber inflammation and/or prolonged posterior chamber inflammation continuing without signs of resolution 28 days after SAR421869 administration.

Criteria for suspending enrolment or further study conduct are defined in the DSMB charter and all events will be reviewed by the DSMB.

In the event of early study termination all patients who have been dosed with SAR421869 will continue to be followed up as per protocol.

8.5 DOSE-LIMITING TOXICITIES

Dosing will stop if a dose-limiting toxicity is encountered in a dosing cohort. Events that constitute a dose-limiting toxicity will be defined in the DSMB charter. Dose-limiting toxicities will include:

- Severe or persistent ocular inflammation.
- Other significant ocular toxicity (eg, large retinal detachment, evidence of direct toxicity).
- Other systemic toxicities (eg, acute allergic reaction).
- Any safety issue that has been identified that adversely changes the benefit/risk balance to study participants.

9 TREATMENT PLAN AND METHODS

9.1 ALLOCATION OF TREATMENTS

Dose Escalation Part A

Patients will be allocated to treatment in the order in which they are enrolled into the study.

Dose escalation or progression to the next patient cohort will be based on safety in the three patients of the previous cohort, including events such as the presence and severity of manifested clinical signs and symptoms, laboratory tests including clinical chemistry, hematology, urinalysis and antibodies. The DSMB will thoroughly review and discuss the results from the previous cohort before proceeding with any subsequent dose escalation. All patients in the previous cohort must be observed for a minimum of 28 days before additional participants receive drug at the next dose level.

Dose Extension (MTD) Parts B and C

The Maximum Tolerated Dose to be used in Parts B and C (Cohorts 4 and 5) of the study will be determined from the dose escalation phase (Part A). Cohort 4 will include only adult patients (≥ 18 years or older) with less advanced RP, while Cohort 5 will provide the opportunity to include pediatric patients 6-17 years of age. Before pediatric patients can be enrolled into the study, the DSMB will review all safety data including the data from Part B, three months after all patients in Cohort 4 have been dosed. An interim report including all available safety data and preliminary efficacy data will be submitted to the regulatory authorities and institutional review boards/ethics committees for review prior to the enrolment of pediatric patients.

9.2 STUDY MEDICATION ADMINISTRATION

9.2.1 Hospitalization

Hospitalization is not required but may be necessary for convenience of some patients. Patients will not take anything by mouth for a minimum of 8 hours prior to surgery.

9.2.2 Intraocular Injection

After informed consent is completed, patients will have baseline assessments and eligibility will be confirmed. Eligible patients will be scheduled for surgery, which will be performed under anesthesia. The study eye will be the eye that in the opinion of the investigator, in consultation with the patient, is the worse seeing eye. In order to select the worse eye the investigator will review the patient historic and Day -1 visual acuity and visual field data and also consider which eye is dominant and any preferences shown by the patient. The study eye will be marked prior to entering the operating room and once in the operating room the study eye will be reconfirmed.

Surgery will be performed under general anesthesia or waking sedation at the surgeon's discretion, with additional periocular/retrobulbar injections according to surgeon and anesthesiologist preferences. Surgery will be performed under sterile conditions in accordance with hospital operating room protocols.

A standard 20- or 23-gauge 3 port pars plana vitrectomy will be performed. If achievable, a posterior vitreous detachment will be induced and the posterior hyaloid will be removed from the posterior retinal surface at least to include the anticipated retinotomy site.

The posterior retina will be examined and the appropriate site for subretinal injection will be identified. Additional details on retinotomy will be provided in study manuals. The final positioning of the retinotomy and subretinal bleb will be determined by the surgeon.

The retina will be approached with a needle loaded with SAR421869. A hydraulically-induced retinotomy will be created and a subretinal bleb created. If the surgeon determines that the bleb is not forming in the correct position, he/she can choose to stop infusing and create another retinotomy. This can be done up to twice until the full volume has been delivered.

At the discretion of the surgeon an air-fluid exchange may be undertaken.

Following the administration of SAR421869, the fundus will be examined by indirect ophthalmoscopy and scleral depression to look for peripheral retinal tears. If there are any peripheral retinal tears, they will be treated with cryopexy and a fluid-air exchange will be done. The vitreous cavity may be filled with the appropriate tamponade at the discretion of the surgeon.

The eye will be patched and the patient will be taken to the post-operative observation area.

For each patient, the following protocol required anti-inflammatory regimen including antibiotics and corticosteroid medications must be administered to reduce the possibility of clinically significant intraocular inflammation after subretinal injection procedure.

- **Immediately following the completion of the subretinal injection procedure administer:**
 - **In Children:** one dose of intravenous methylprednisolone 1 mg/kg for patients ≥ 50 kg or 0.5 mg/kg for patients < 50 kg. Maximum corticosteroid dose not to exceed 80 mg for children < 16 years.
 - **In Adults:** one dose of intravenous methylprednisolone 1 mg/kg.
 - At the discretion of the surgeon, a subconjunctival injection of corticosteroids (eg, Dexamethasone 5 to 10 mg) and/or a subconjunctival injection of antibiotics may be given.
- **Starting (post-operative) Day 1 administer/initiate:**
 - **In Children:** oral prednisone 1 mg/kg/day for patients ≥ 50 kg or 0.5 mg/kg/day for patients < 50 kg daily for 5 days, then reduce dose to 0.5 mg/kg/day for patients ≥ 50 kg or 0.25 mg/kg/day for patients < 50 kg daily for 5 days, then reduce dose by 10 mg daily until the corticosteroid taper is complete. Maximum corticosteroid dose not to exceed 80 mg for children < 16 years.

- **In Adults:** oral prednisone 1 mg/kg/day for 5 days, then reduce dose to 0.5 mg/kg/day for 5 days, then reduce dose by 10 mg daily until the corticosteroid taper is complete.
- Topical broad-spectrum antibiotic (eg, ofloxacin, ciprofloxacin, moxifloxacin, trimethoprim-polymyxin B or similar) QID for 7-10 days.
- Topical prednisolone acetate 1% (or similar) 4 times a day (QID) for 7-10 days, then three times a day (TID) for 7-10 days, then two times a day (BID) for 7-10 days, then once daily (QD) for 7-10 days. (Note: The frequency of the topical corticosteroid drops and the timing for the start of the taper may be adjusted as needed in response to the patient's manifestation of post-operative inflammation with the goal of resolving the post-operative ocular inflammatory response within 28 days after the surgical procedure).
- A topical steroid ointment (eg, sterdex, tobradex or similar) may also be given at bedtime (qhs) for 7-10 days at the discretion of the surgeon.

Intraocular inflammation worsening during the course of treatment with the protocol defined anti-inflammatory regimen (see [Section 9.3.12](#) Medication, Adverse Event and Concomitant Medication Review) or persisting or occurring after the completion of the above protocol defined anti-inflammatory regimen must be recorded as a post-surgical adverse event.

For the management of intraocular inflammation persisting or occurring after the completion of the above post-surgical anti-inflammatory regimen or worsening during the course of the regimen see [Section 9.3.12](#) Specific Procedures - Medication, Adverse Event and Concomitant Medication Review

9.2.3 Positioning of the Subretinal Bleb

The placement of the retinotomy site and subretinal injection will be detailed in study manuals.

9.2.4 SAR421869 Preparation

SAR421869 will be provided in 100 µL aliquots in 0.3 mL Type I borosilicate glass 'V' vials with a butyl stopper and aluminum crimp seal. Each vial of SAR421869 will be issued in a white plastic tamper proof container secured in packaging. The vial and plastic tamper-evident container will be labelled appropriately.

Further details of the preparation of SAR421869 for administration are provided in the study pharmacy manual.

9.2.5 SAR421869 Administration

All disposable surgical supplies; including gloves, masks, gowns, dressings and swabs used during the surgical procedure will be destroyed by incineration according to hospital policy at the end of the operation. The first dressings removed from the patient's wounds following surgery will also be disposed of by incineration.

9.2.6 Post-Surgical Monitoring

Vital signs will be documented 30 and 60 minutes after the end of surgery. After 60 minutes, if the patient is feeling well and able to tolerate food and drink, he/she will be discharged. Before discharge, blood and urine samples will be obtained for PCR assay for viral particles.

9.2.7 Concurrent Treatments

Concurrent treatments for any concurrent diseases are permitted in this protocol and will be recorded in the CRF.

9.2.8 Study Conduct Specific to Children and Adolescents

It is important to note that children and adolescents will not be enrolled in the current study unless data from adult patients treated with SAR421869 demonstrate that the risk is justified by an anticipated benefit to the patients.

The process of informed assent of children/ adolescents and the consent of their parents, guardians or other legal representatives will ensure that all parties understand the unique risks associated with gene therapy as well as the specific risks associated with ocular gene therapy. Moreover, the process will ensure that all parties understand the risks of participating in early clinical research where the safety and efficacy of a therapy may not have been fully established. The management of children and adolescents will be approached on an individual patient basis within the constraints of the protocol and the necessary procedures and monitoring to ensure safety. The patient and parents/legal guardians will be fully informed and consulted at all stages of the research and concerning all decisions regarding the management of the individual during subsequent follow-up.

Signed and dated written informed consent must be obtained from the patient (or assent in the case of minors from their legal guardian/representative), in accordance with the local regulations.

As in adults, the following procedures will be followed when including children and adolescents in the protocol:

- To ensure effective monitoring of both vector and product, biodistribution and immunology samples will be collected at the same intervals as in adult patients.
- Children and adolescents will enter the open label long-term follow-up protocol designed to monitor the long-term safety of patients treated with SAR421869.

Appropriate measures will be implemented to minimize any pain or discomfort associated with study procedures in children, including administering SAR421869 under general anesthesia if necessary, and where appropriate providing in-patient hospitalization for postoperative management.

- The administration of SAR421869 to children of less than 12 years will be under general anesthesia with neuromuscular paralysis and controlled ventilation.
- Postoperative nausea and vomiting will be managed proactively through prophylactic use of anti-emetics.

- Perioperative analgesia will be administered (eg, subtenon lidocaine block), at the time of surgery and oral post-operative analgesia will be available to minimize any discomfort.
- The surgeons and anesthesiologists will be experienced in pediatric ocular surgery and anesthesia.
- The ophthalmic monitoring procedures included in this protocol are non- invasive and as such involve minimal discomfort to the patient. Pupil dilatation is necessary for effective examination and this can result in some sensitivity to light. In general, these examinations are well tolerated and in this vulnerable group any discomfort will be kept to a minimum.
- Particularly for the younger age patients, hospitalization may be necessary for some procedures, which would normally be managed in an out-patient setting for adults. Accommodation and logistic assistance will be provided to family members/care givers to ensure they can be close to children in the event of hospitalization.
- Routine phlebotomy for safety laboratory blood samples will be kept to a minimum. All routine safety bloods will be taken at screening. However, subsequent hematology and chemistry evaluations will be as clinically indicated and at the discretion of the investigator. Blood draws will be performed by personnel adequately trained and knowledgeable in phlebotomy techniques in pediatric patients.
- Chest X-ray and ECG will not be required at screening unless considered clinically indicated by the investigator or anesthesiologist (non-compulsory investigations in children are indicated in [Section 3](#)).

